Research Summary

1. Protocol Title:

Comparison of TAP, Anterior QL, or ESP Block for Elective Cesarean Section

2. Purpose of the Study:

The purpose of this prospective single center, randomized study is to determine if ultrasound guided Quadratus Lumborum (QL) and Erector Spinae Plane (ESP) blocks decrease opioid consumption compared to Transversus Abdominis Plane (TAP) in subjects undergoing elective cesarean section. Total opioid consumption and pain scores will be monitored for 48 hours postoperatively.

3. Background & Significance:

Cesarean section is an invasive surgery that can lead to significant postoperative pain. Well controlled postoperative pain in this specific patient population can help minimize the effect of surgery on a new mother's ability to care for her newborn and ease the transition back home, as well as allay any concerns regarding transfer of opiates through breastfeeding.

The typical anesthetic plan involves a spinal anesthetic or combined spinal epidural anesthetic as the primary anesthetic for the procedure followed by a combination of oral pain medications, including opioids, to control pain postoperatively. Side effects from opioid use, including nausea, vomiting, sedation, or respiratory depression, can hinder a new mother's ability to fully participate in the care of her newborn. Additionally, some women are leery to take opioids if they are breastfeeding for fear of transfer to their newborn [1]. Despite widespread postoperative prescription of opioids, women report poor pain control after cesarean section [2-4]. As part of a larger public health concern, unused postoperative opioids can be detrimental and the possibility of persistent opioid use after surgery is feasible in this patient population [5].

TAP blocks have been utilized for years to help control incisional pain after abdominal surgeries, including cesarean section [6, 7]. However, it is not without limitations and there is some question regarding efficacy [8]. TAP blocks often decrease somatic pain, but do not impact visceral pain which can contribute to uncontrolled postoperative pain after cesarean section. Additionally, it has been shown that TAP blocks do not improve analgesia when patients are already receiving intrathecal morphine[9].

With newer truncal blocks like anterior quadratus lumborum (QL) and erector spinae plane (ESP) blocks coming into practice, it will be helpful to identify which, if any, of the three blocks can benefit this unique patient population.

Studies involving earlier variations of the quadratus lumborum block have shown to be successful after cesarean section [10, 11]. At Duke University Hospital, we most commonly perform the anterior variation of the QL block which has not specifically been studied in this patient population. However, case series have demonstrated success in other abdominal procedures [12].

Erector spinae plane blocks were initially used to treat pain from rib fractures and thoracotomies, but have now been shown to be effective for open abdominal procedures [13-15]. However, there has only been one case report to date using an ESP block for cesarean section [16].

This study aims to answer if QL or ESP can impact postoperative opioid use and pain scores after cesarean section compared to TAP block.

4. Design & Procedures:

The typical anesthetic for cesarean section at Duke University Hospital includes a spinal or combined spinal epidural anesthetic with intrathecal dosing of 1.4-1.6 mL bupivacaine HCI 0.75%, 15 mcg fentanyl, and 150 mcg morphine. If the epidural component of a combined spinal epidural anesthetic is used, the subject will be withdrawn from the study. Patients also receive rectal acetaminophen 975 mg prior to incision, intravenous (IV) ondansetron 4 mg, metoclopramiden10 mg, famotidine 20 mg and dexamethasone 4 mg intraoperatively, and IV ketorolac 15 mg prior to skin closure. There will be no change to this typical practice.

Patients who consent to be in this study will be randomized to receive one of three truncal nerve blocks using an online randomization program by the study PI ([name]): (1) ultrasound-guided bilateral classic TAP block; (2) ultrasound-guided bilateral anterior QL (also known as transmuscular or QL type 3) block; (3) ultrasound-guided bilateral ESP block at the level of T9. These nerve blocks will be performed after delivery and within one hour of skin closure with 25 mL of 0.2% ropivacaine with epinephrine 1:400,000 per side. Nerve blocks will be performed by a dedicated and trained group of regional anesthesiologists. This non-blinded regional anesthesiologist will save an ultrasound image after local anesthetic administration while the needle is still in position on each side. The study team will review these images to ensure a high quality of block performance.

Patients will have standard postoperative pain medication orders, including acetaminophen 975 mg PO Q6H for 4 days (scheduled, starting 6 hours after intraoperative rectal dose), ketorolac 15 mg IV Q6H for 24 hours (scheduled, starting 6 hours after intraoperative dose), ibuprofen 600 mg PO Q6H for 3 days (scheduled, starting 24 hours after first dose of ketorolac) and oxycodone 5-10mg PO Q3-4H PRN for 4 days. If patients are unable to tolerate oral medication or oxycodone is insufficient, rescue medications may be ordered: IV morphine 1-2 mg or IV hydromorphone 0.3-0.5 mg Q4H as needed. There is no change from the standard postoperative order sets used for patients after cesarean section.

Subjects' verbal pain scores at rest and with movement as well as opioid consumption will be recorded at 2, 6, 24, and 48 hours postoperatively. The validated Obstetric Quality of Recovery-11 (ObsQoR-11) score will also be assessed at 24 and 48 hours postoperatively [17]. Additionally, the amount of antiemetics and antipruritics used will also be recorded at the above time points. These scores will be entered into a Duke University Hospital REDCap database. Subjects will also be sent a survey assessing their satisfaction with pain control one week after discharge via email or telephone. This information will be collected via Duke University Hospital REDCap.

5. Selection of Subjects:

Research Summary Version Date: 8/27/2018 Protocol ID: Pro00100742 Patients undergoing elective cesarean section will be identified the day prior to surgery. Patients will be contacted via telephone by a member of the study team the day prior to surgery to confirm eligibility and, if eligible and interested, the study will be explained. Inclusion and exclusion criteria will be assessed through self-reporting by the subjects and review of patient chart on EPIC. Patients will be given the opportunity to ask initial questions about the study over the phone. Patients interested in participating will have the protocol fully explained and written informed consent will be obtained on the day of surgery prior to the procedure. The patient's care team, including attending surgeons, attending anesthesiologists, anesthesia residents, and nurse anesthetists will be informed of the patient's inclusion via secure email with specifics for the case.

Inclusion Criteria:

- 1) American Society of Anesthesiologists (ASA) Physical Status 1-3
- 2) Age greater than or equal to 18 years
- 3) Scheduled cesarean section
- 4) English speaking

Exclusion Criteria:

- 1) ASA Physical Status 4-5
- 2) Diagnosis of chronic pain
- 3) Chronic opioid use (opioid use in the past 3 months)
- 4) Preoperative use of SSRIs (Celexa, Lexapro, Prozac, Paxil), SNRIs (Cymbalta, Effexor), gabapentin, or pregabalin (Lyrica)
- 5) Inability to cooperate with or understand protocol
- 6) Inability to communicate pain scores or need for analgesia
- 7) Infection at the site of block placement
- 8) Intolerance or allergy to local anesthetics
- 9) Neurologic deficit or disorder
- 10) Blood thinning disorder or taking anticoagulant medication
- 11) BMI > 50 kg/m²
- 12) Suspected or known addiction to or abuse of illicit drug(s), prescription medicine(s), or alcohol within the past 2 years
- 13) Uncontrolled anxiety, schizophrenia, or other psychiatric disorder that, in the opinion of the investigator, may interfere with study assessments or compliance
- 14) Current or historical evidence of any clinically significant disease or condition that, in the opinion of the investigator, may increase the risk of surgery or complicate the subject's postoperative course

6. Subject Recruitment & Compensation:

Only patients who are having elective cesarean sections are eligible for this study. We will not bias any demographic groups in identifying patients eligible for this study. A total of 75 patients will be consented from Duke University Hospital. An IRB approved phone script will be used to discuss the study with eligible patients. Patients will not receive any additional compensation for enrollment in this study.

7. Consent Process:

Potential subjects will be contacted and screened the day prior to surgery via telephone. If the patient is interested in the study, the consent process will take place in a private preoperative room on the Labor and Delivery ward prior to surgery. The consent process will be conducted by a member of the research team. Throughout the consent process, measures will be taken to maintain privacy, such as conducting face-to-face conversations in private rooms. As much time as necessary will be spent with each potential subject to sufficiently explain and answer all questions, and address all concerns they may have in regard to the study and/or consent process. Under HIPAA waiver, the study team will identify potential subjects from clinic schedules, OR schedules, and Maestro Care.

8. Subject's Capacity to Give Legally Effective Consent:

Patients who do not have the capacity to give legally effective consent will not be approached for participation in this study.

9. Study Interventions:

See 4 above.

10. Risk/Benefit Assessment:

Patients will be consented regarding the standard risks associated with regional anesthesia. These standard risks include: minor pain or discomfort; bruising; infection at the needle insertion site; injury to arteries, veins, or nerves affecting the abdomen, back, or legs; residual numbness, weakness, or paralysis; headache; muscle soreness. If patients are allergic to the local anesthetic (ropivacaine) or have an adverse drug reaction, they could possibly have a reaction that is severe enough to cause cardiac arrest and/or respiratory arrest. If there is injection of local anesthetic into a blood vessel, patients could possibly have loss of consciousness, seizure, or cardiac arrest.

There have been rare case reports of hip or knee weakness after quadratus lumborum block. Therefore, patients will be encouraged to have someone with them to help them of bed the first time after the nerve block is performed.

Benefits include contributing to general knowledge to improve future patient care. Benefits also include potential analgesic benefit, decreased pain scores, and improved patient satisfaction. Conversely, this study may show no benefit of the block, thereby invalidating the technique.

11. Costs to the Subject:

Subjects will not incur any additional costs to participate in the study. A MaestroCare build will be created to ensure that any subjects are not charged for researched related procedures, equipment, or medications.

12. Data Analysis & Statistical Considerations:

A randomized trial of 75 subjects (25 per group) will provide 80% power to detect a 35% decrease in opioid use between treatment groups in a t-test at an alpha level 0.017 utilizing Bonferroni's correction,

(parametric), Mann-Whitney U Test (nonparametric), or repeated measures ANOVA as appropriate. Sample size and power calculations were performed using PASS v15 (NCSS, LLC. Kaysville, Utah).

Patient and surgical characteristics will be summarized by standard descriptive statistics and will be compared between groups using t-tests, ANOVA, or Wilcoxon sum ranked tests as appropriate. We will report odds ratios, 95% confidence intervals, and p-values to assess significance and clinical importance of the observed treatment effect. Additional measures of treatment efficacy (pain scores, ease of mobility, overall pain experience) will be summarized overall and between groups to further characterize the treatment effect in this population.

13. Data & Safety Monitoring:

In accordance with federal regulations the PI will monitor for, review, and promptly report to the IRB, appropriate institutional officials, sponsor, coordinating center and the appropriate regulatory agency head all unanticipated problems involving risks to subjects or others that occur in the course of a subject's participation in a research study (45 CFR 46.103(b)(5)(i) and 21 CFR 56.108(b)(1)), all AE reports will be reported per the DUHS IRB policies. PI will be monitoring all AEs and submitting reports to the IRB per DUHS IRB policy.

14. Privacy, Data Storage & Confidentiality:

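### Does the silence on who is masked, and on who records pain and recovery scores, undermine the comparison of the three blocks?

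*Combined protocol and SAP*

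**What the plan says.** Section 4 has the principal investigator randomize each patient, through an online program, to one of three blocks: "ultrasound-guided bilateral classic TAP block", a bilateral anterior QL block, or "ultrasound-guided bilateral ESP block at the level of T9". All three use the same volume and concentration of ropivacaine with epinephrine on each side. The one statement about masking is "This non-blinded regional anesthesiologist will save an ultrasound image after local anesthetic administration". The study team then reviews those images for quality.

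The outcome sentences are passive. Section 4 states that "verbal pain scores at rest and with movement as well as opioid consumption will be recorded at 2, 6, 24, and 48 hours postoperatively", that the ObsQoR-11 "score will also be assessed at 24 and 48 hours postoperatively", and that subjects are sent a "survey assessing their satisfaction with pain control one week after discharge via email or telephone". No recorder is named for any of these. Postoperative orders are the same in every arm and include "oxycodone 5-10mg PO Q3-4H PRN for 4 days", with intravenous rescue available.

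On what patients know beforehand, Section 5 says: "Patients interested in participating will have the protocol fully explained". It adds that surgeons and anesthesia staff are emailed about a patient's inclusion and the details of the case.

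Section 12 bases the sample size on opioid use, with 75 subjects and 25 per group. It treats pain scores as additional measures, summarized to describe the effect further.

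**The concern.** Calling one person non-blinded implies that somebody else is blinded, yet the plan never says who. Masking cannot simply be presumed. The principal investigator runs the randomization, and the study team sees images taken with the needle in place. Nothing separates either from the people who collect outcomes. Each patient receives one type of block, no sham is described, and the blocks are different techniques, so a patient to whom the protocol has been explained might work out her arm.

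She is also the source of the pain scores, the ObsQoR-11 and the satisfaction answers, and her requests drive the as-needed oxycodone, which has a 5-10 mg range. If patients or recorders knew the arm and expected more from one block than another, part of any QL-TAP or ESP-TAP difference could be expectation and not analgesia. The Background could feed such an expectation: Section 3 cites a finding that TAP adds nothing once intrathecal morphine is given, and the standard anesthetic in Section 4 contains 150 mcg of it.

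**Working it through.** The plan prints no figure on masking, so there is none to reproduce. Two checks are possible: the volume of data involved, and what the text supports about each route by which the arm could become known.

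**Counts.** Inputs are 75 subjects, 25 per arm (Section 12), and the assessment times in Section 4.

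- Verbal pain scores: 75 × 4 times × 2 conditions = 600; per arm 25 × 4 × 2 = 200.
- ObsQoR-11: 75 × 2 times = 150; per arm 25 × 2 = 50.
- Opioid entries: 75 × 4 = 300; per arm 25 × 4 = 100.
- One-week survey: at most 75.

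These are maxima. Section 6 counts 75 as consented, and Section 4 withdraws a subject if the epidural part of a combined technique is used. They describe the schedule and would be identical in a perfectly masked trial, so they say nothing about bias. The documents contain no input from which a bias could be computed.

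**Routes to the arm.**

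| Person | What the text says | What follows |
|---|---|---|
| Principal investigator | Runs the randomization | Knows the arm; not said to record outcomes |
| Operator | Described as non-blinded | Knows the arm; not said to record outcomes |
| Study team | Reviews block images | May learn the arm; separation from outcome recording not stated |
| Surgeons and anesthesia staff | Emailed about inclusion and the case | Whether the arm is named is not stated; postpartum nurses are not listed |
| Patient | Protocol explained beforehand; neuraxial anesthetic; no sham described | May or may not infer the arm |
| Recorder, analyst | Not named | Unknown |

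The strongest routes in the text are the randomization by the principal investigator and the image review. Both are met by ordinary practice: someone who has seen neither collects the scores. The patient route is weaker than it looks. Apart from the T9 level for ESP, the protocol does not describe needle sites, positioning or dressings, and the neuraxial anesthetic may dull sensation where the needle enters.

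**Expectation.** The Background reports one literature result about TAP with intrathecal morphine. It does not say that QL or ESP does better in that setting. Section 3 leaves open whether any of the three blocks helps, notes that anterior QL is unstudied in this population, and cites a single case report for ESP. Section 10 allows that no benefit may be found. The purpose in Section 2 is directional, but that is a hypothesis. Nothing says that patients are told TAP is inferior.

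**Which outcome is exposed.** Opioid use carries the sample size. It can respond to patient request and staff discretion, but every arm has an active bilateral block of the same drug and volume under the same orders, so there is no untreated arm to recognise. The patient-reported measures are more exposed, and Section 12 gives them a descriptive role.

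**The case for a change.** The best case for a change is that the outcomes are subjective, the principal investigator and study team can know the arm, no barrier is written down, and a sentence or two would settle it. Without that, a reader cannot judge how far a difference in pain or recovery scores reflects the block itself.

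Part of this stands. The protocol does not say who is masked or who records, and a report of the trial must say both. The consent pages and telephone script are not in the public text, so wording there cannot be excluded.

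The rest does not carry a change. Writing down masking status records what staff do without altering any estimate or test. A recorder who has not seen the allocation is sensible, but the protocol gives no staffing from which to judge whether one is always available, and such a recorder does not alter what a patient says about her own pain. Closing the patient route would need sham procedures, which would be a different trial. Specifying the medication record as the source of opioid totals, or editing the inclusion email, would answer no fault visible in the text.

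**Conclusion.** No change to the plan follows. This is a gap in description that the trial team can fill sensibly: the operator is singled out as non-blinded, which points to masking of others, and no stated rule would produce a wrong result. No size of bias can be given, because the documents supply none and show none. The planned maxima of 600 pain scores and 150 ObsQoR-11 scores measure workload only.

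The conclusion assumes that scores are in practice collected by people who have not seen the allocation or the block images, and that opioid use remains the main comparison with identical orders in all arms. If the scores were in fact taken by people who knew the arm, the patient-reported differences would need to be read with that caution, and the report should say so.

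### Cheap improvement, not an error: replacing single-step Bonferroni with a step-down test over the same three pairs gains power at the same 5% family-wise error

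*Combined protocol and SAP*

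**What the plan says.** Section 12 (Data Analysis & Statistical Considerations) states 80% power with 75 subjects, 25 per group, for a "35% decrease in opioid use between treatment groups in a t-test at an alpha level 0.017 utilizing" Bonferroni's correction. In the copy read here the text breaks off just after that and resumes with a list of tests ending "Mann-Whitney U Test (nonparametric), or repeated measures ANOVA as appropriate". The number of comparisons and the 5% family-wise level are not written out. The readable text mentions no step-down, closed or gatekeeping procedure.

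On reporting, Section 12 says: "We will report odds ratios, 95% confidence intervals, and p-values to assess significance and clinical importance of the observed treatment effect".

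Two readings of the comparison family have support:

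- **Three pairs.** This fits the title, "Comparison of TAP, Anterior QL, or ESP Block for Elective Cesarean Section", and the Section 3 remark that "it will be helpful to identify which, if any, of the three blocks can benefit this unique patient population".
- **Two pairs.** Section 2 asks whether QL and ESP "decrease opioid consumption compared to Transversus Abdominis Plane (TAP) in subjects undergoing elective cesarean section", and the closing sentence of Section 3 also uses TAP as the comparator.

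On numbers, Section 6 says "A total of 75 patients will be consented", the same 75 as in the power statement. Section 4 adds: "If the epidural component of a combined spinal epidural anesthetic is used, the subject will be withdrawn from the study".

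**The concern.** Nothing here is invalid. Single-step Bonferroni holds each of the three tests to 0.05/3 even after one of them has been rejected. Holm starts at the same 0.05/3 and then relaxes to 0.05/2 and 0.05, with the same strong control of family-wise error under any dependence between the tests. Single-step Bonferroni therefore gives up power without a better error guarantee.

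Three arms make this relevant whenever the blocks differ at all. If any one pair truly differs, at least two of the three pairs must differ, so there is always a second true difference that the later steps can help to find.

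The planned 80% power is not at risk, because the stricter alpha is built into the sample size. What is at stake is the chance of confirming the second difference. For this trial's stated purpose, that means showing both QL and ESP better than TAP when both work. No dropout allowance is stated, so power that needs no extra patients is useful.

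**Working it through.** **Inputs from the protocol.** Three arms (Section 4); 25 per group, 80% power, a 35% decrease, t-test, alpha 0.017 with Bonferroni (Section 12). Not given: SD, control mean, sidedness. Assumed: two-sided pairwise t-tests, normal data, equal SDs.

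**Step 1: the alpha.** 0.05/3 = 0.01667, which rounds to 0.017; 0.05/2 = 0.025 does not. So 0.017 corresponds to three pairs. Because 3 × 0.017 = 0.051, a step-down rule should use 0.05/3 unrounded.

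**Step 2: the plan's power.** The 80% cannot be reproduced without an SD, so the standardised difference d was solved from it. With noncentral t, 48 degrees of freedom and noncentrality d × √(25/2), power of 0.80 at alpha 0.017 gives d = 0.941. The implied coefficient of variation (CV) is 0.35/0.941 = 0.372. At this d, one pair has power 80.0% at 0.017, 84.1% at 0.025 and 90.3% at 0.05. The last two are Holm's second- and third-step levels.

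**Step 3: the procedures compared over the same three pairs.**
- Plan: each p-value against 0.017.
- Holm: ordered p-values against 0.05/3, 0.05/2, 0.05, stopping at the first non-rejection.
- Shaffer's three-arm version: 0.05/3, then 0.05, 0.05. This is valid because once one pair truly differs, at most one of the other two can be equal.

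**Step 4: results** (1,000,000 simulated trials per scenario, 25 per arm, d = 0.941):

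| Scenario and quantity | Plan | Holm | Shaffer |
|---|---|---|---|
| Both blocks work: power per TAP comparison | 80.0% | 82.8% | 86.5% |
| Both blocks work: both shown better than TAP | 68.7% | 74.4% | 81.8% |
| Both blocks work: at least one shown better than TAP | 91.3% | 91.1% | 91.1% |
| Both blocks work: false QL vs ESP | 1.7% | 3.8% | 5.0% |
| Only QL works: QL vs TAP | 80.0% | 82.9% | 86.5% |
| Only QL works: QL vs ESP | 80.0% | 82.8% | 86.5% |
| Only QL works: false ESP vs TAP | 1.7% | 3.8% | 5.0% |
| No differences: family-wise error | 4.5% | 4.4% | 4.4% |

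The plan's 0.2-point edge in the third row comes from rounding 0.05/3 up to 0.017. If the arms are evenly spaced (0, d, 2d), all three differences are found in 61% of trials under the plan and 81% with Holm.

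**Step 5: sensitivity, both blocks working** (plan / Holm / Shaffer):
- CV 0.30, power per comparison: 94.7 / 96.0 / 97.4%.
- CV 0.40: 73.1 / 76.1 / 80.4%.
- CV 0.50: 50.6 / 53.5 / 58.3%.
- CV 0.80: 18.9 / 20.0 / 22.5%.
- Over CVs of 0.30 to 0.80, the gain per comparison is 1.2 to 3.1 points with Holm and 2.7 to 7.7 with Shaffer. The gain for both shown is 2.5 to 6.4 and 5.5 to 15.5 points.
- 22 evaluable per arm (assumed), same d: per comparison 73.6 / 76.7 / 81.0%; both shown 60.2 / 66.6 / 75.2%.
- Mann-Whitney on lognormal data (assumed CV 0.5, 35% lower, 25 per arm): per comparison 73.4 / 76.9 / 81.0%; both shown 59.9 / 66.9 / 75.2%; family-wise error with no differences 4.0% for all three.

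**The case against.** **The analysis rule is partly missing.** The 0.017 appears only in the power sentence, and the text after it is lost. An omnibus analysis cannot be strictly excluded: an F-test at 0.05 followed by pairwise tests at 0.05 would give about 88% per TAP comparison and 83% for both, with family-wise error of about 5% in three arms. It stands that the single-step rule is inferred. But an F-test gate sits badly with a stated Bonferroni correction, which it would make unnecessary.

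**The family may be the larger issue.** The stated purpose names only the two comparisons with TAP. Plain Bonferroni over those two, at 0.025 each, gives 84% per comparison, 74.5% for both and 94% for at least one if both blocks work. That matches or beats Holm over three pairs. This stands as an alternative, but it drops QL vs ESP from the confirmatory set. Holm over three pairs keeps every comparison that 0.017 implies.

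**The gain is modest.** Holm adds about 3 points per comparison and 6 for both; the larger figures belong to Shaffer. The first rejection becomes no likelier, and plan power itself runs from 95% to 19% over CVs of 0.30 to 0.80, so the unknown SD matters more than the procedure. All of this stands and bears on priority.

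**Bonferroni has matching simultaneous intervals** (98.3% each). Holm and Shaffer have no simple equivalent, and Section 12 uses intervals to judge clinical importance. This is a real, small cost.

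**The outcome must be pinned down first.** Section 2 refers to total opioid use over 48 hours, while Section 4 records it at 2, 6, 24 and 48 hours. Holm over three pairs is well defined only for one named outcome and test. That is true of Bonferroni at 0.017 as well.

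**Conclusion.** The point holds as a recommended improvement, not as a fault. That Holm rejects everything Bonferroni at 0.05/3 rejects, at the same 5% family-wise guarantee, does not depend on the SD or on the distribution, provided the pairwise p-values are valid.

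The size does depend on assumptions: a three-pair family inferred from 0.017, two-sided tests, normal data with equal SDs, and the CV of about 0.37 implied by the stated power. On those, Holm adds about 3 points per true difference and about 6 points for confirming both blocks against TAP. Shaffer's version adds about 6.5 and 13 points. Neither raises the chance of a first rejection, and 25 per group need not change. Confidence is medium, because the analysis sentence is incomplete in the copy read and no SD is given.

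**What to change.** Before outcome data are seen, add one sentence to Section 12: the three pairwise p-values for the single opioid-use outcome on which the power is based, from the planned t-test or Mann-Whitney test, will be judged by Holm's procedure at 0.05/3, 0.05/2 and 0.05 in order, stopping at the first non-rejection. The same sentence could instead name Shaffer's three-arm version (0.05/3, then 0.05, 0.05). It should name the outcome and say that the procedure does not cover repeated testing across time points. Label the planned 95% intervals as unadjusted.

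**Cost:** that sentence and the label. The sample size, procedures, data collection and set of confirmatory comparisons are unchanged. The loss is simple simultaneous intervals that match the test decisions.

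**Optional, with a real trade-off:** restrict the primary family to QL vs TAP and ESP vs TAP with Holm (0.025, then 0.05). This follows the purpose sentence. Power per comparison is 84% if only that block works and 88% if both do; if both work, it is 83% for confirming both and 94% for at least one. QL vs ESP, which has 80% power under the plan when only one of the two blocks works, would become secondary.

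### Section 12 offers repeated measures ANOVA as its only readable longitudinal method and gives no rule for missed assessments; for the pain scores, a mixed model on all available data would lose less.

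*Combined protocol and SAP*

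**What the plan says.** Section 4 (Design & Procedures) states that each woman's "verbal pain scores at rest and with movement as well as opioid consumption will be recorded at 2, 6, 24, and 48 hours postoperatively". Antiemetic and antipruritic use follows the same four times. ObsQoR-11 is taken twice, at 24 and 48 hours.

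Section 12 (Data Analysis & Statistical Considerations) bases the sample size on opioid use: "A randomized trial of 75 subjects (25 per group) will provide 80% power", "in a t-test at an alpha level 0.017 utilizing Bonferroni's correction". The next readable text is the end of a list of methods: a parametric test whose name is lost in the extracted text, then "Mann-Whitney U Test (nonparametric), or repeated measures ANOVA as appropriate". Repeated measures ANOVA is the only method in the readable text that handles several times per woman. Pain scores appear later in the section among the additional efficacy measures, to be summarised by group, with no model named.

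No section gives a missing-data rule, an analysis population or a mixed model. Section 6 leaves no allowance for loss: "A total of 75 patients will be consented from Duke University Hospital".

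**The concern.** A verbal score due at a fixed hour is easy to miss: the woman may be asleep, busy with the newborn, or close to discharge at 48 hours. Classical repeated measures ANOVA works on complete rows, so a woman scored at 2, 6 and 24 hours but not at 48 contributes nothing. With 25 women per arm and no spare recruitment, that costs precision on the pain outcomes. It can also bias the comparison if the women who miss a score differ from those who do not.

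The group test from such an ANOVA is an overall comparison of three arms. The questions in Sections 2 and 3 are QL against TAP and ESP against TAP, so the pairwise contrasts need to be named for the repeated outcomes as well.

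**Working it through.** **The plan's own figure.** The stated alpha is consistent with three pairwise comparisons: 0.05/3 = 0.0167, rounded to 0.017. The sample size cannot be reproduced forward, because no mean or SD is given. Solving backwards, 25 per arm with 80% power at two-sided 0.017 implies a standardised difference of 0.941 (noncentral t). A 35% decrease then corresponds to an SD of 0.35/0.941 = 37% of the comparator mean. This calculation is for a t-test on opioid use. It is not needed for the results below.

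**Inputs for the check.**
- From the documents: 75 women, 25 per arm (Section 12); four scoring times (Section 4). Planned scores per pain outcome: 75 × 4 = 300.
- Assumed: m, the chance that any one score is missed, at 2%, 5% and 10%. The documents give no value.
- Assumed: equal correlation between times, from 0.3 to 0.7.

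**Case A: misses independent across times.** The share of women with all four scores is (1 − m)^4. Complete-case analysis keeps 75(1 − m)^4 women and 300(1 − m)^4 scores. A mixed model uses all 300(1 − m) observed scores.

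| m | (1 − m)^4 | Women kept, complete-case | Scores kept, complete-case | Scores used, mixed model |
|---|---|---|---|---|
| 2% | 0.922 | 69 | 277 | 294 |
| 5% | 0.815 | 61 | 244 | 285 |
| 10% | 0.656 | 49 | 197 | 270 |

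For complete cases, the standard error of the time-averaged arm difference grows by roughly 1/√((1 − m)^4) = 1/(1 − m)^2, which is 1.04, 1.11 and 1.23. Averaging over simulated patterns of misses, where the number of complete women varies by chance, gives 1.04, 1.11 and 1.25. For the mixed model, generalised least squares with arm-by-time means and the same simulated patterns gives:

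| m | Complete-case SE ÷ full-data SE | Mixed-model SE ÷ full-data SE |
|---|---|---|
| 2% | 1.04 | about 1.00 |
| 5% | 1.11 | 1.00 to 1.01 |
| 10% | 1.25 | 1.01 to 1.03 |

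The ranges cover correlations from 0.7 to 0.3. The covariance was treated as known, so the small cost of estimating it is not included.

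**Case B: all misses fall in the same women.** Complete-case analysis keeps 75(1 − m) = 73.5, 71.25 or 67.5 women, about 73, 71 or 67. The standard error ratio is 1/√(1 − m) = 1.01, 1.03 or 1.05. Women with no scores add nothing to a mixed model, so the two methods agree here. They also agree in this respect when no score is missed.

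**ObsQoR-11.** With two times, the share of complete women under independent misses is (1 − m)^2 = 0.960, 0.903 or 0.810, so the loss is smaller.

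**The case against.** The strongest reply is that the plan does not commit to what is criticised. Repeated measures ANOVA is one of several options to be used as appropriate. The start of its sentence is missing from the extracted text, and nothing readable ties it to pain scores. Dropping incomplete women is a property of the classical form, and the same label is sometimes used for mixed-model fits. A reader might infer that the plan excludes every woman with one missed score; the documents do not say so. This part of the reply stands, and the point is therefore conditional on the classical form being used.

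A reader might also infer that the main comparison loses power. If the standardised difference of 0.941 were carried over to a complete-case analysis, power would fall from 80% to about 76%, 69% and 57% at m = 2%, 5% and 10% under independent misses. Those figures borrow an effect size from the opioid t-test. Total 48-hour opioid use is one value per woman, and no power is claimed for the pain scores. With clustered misses the same calculation gives 79%, 77% and 75%. It is not a loss on any planned test.

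Three further objections hold:
- The one loss the plan does foresee, withdrawal when the epidural component is used (Section 4), removes whole women, so a mixed model does not help there.
- Sphericity matters for the time and arm-by-time tests, not for the test between arms, so it adds little here.
- Averaging running opioid totals would overweight early doses, but no section proposes that. It is only a reason to state that opioid use is a single total.

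The reply does not make the classical method preferable. Under the assumptions of the check it is no more precise than a mixed model, and it is less precise whenever a woman misses only some of her scores. The loose wording also leaves the choice of method, and the handling of missed scores, open until the data have been seen.

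**Conclusion.** The point holds as a conditional one about the repeated additional outcomes, mainly pain at rest and pain with movement. If the classical form is used, the standard error of the time-averaged difference rises by about 4%, 11% or 25% when 2%, 5% or 10% of scores are missed independently, against at most about 3% for a mixed model. If the misses all fall in the same women, the rise is about 1%, 3% or 5% under either method. The true figure depends on a rate and pattern that the documents do not give, and with only 48 hours of follow-up it may be negligible.

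The powered t-test on opioid use is not affected. Nor would a mixed model remove all bias: it is valid if data are missing at random. If a score is missed because of how the woman feels at that moment, missingness depends on the unseen score, and both methods can be biased. The change is worth making because it costs little and settles a choice that the plan leaves open.

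**What to change.** In Section 12:
- For pain at rest and pain with movement, replace repeated measures ANOVA with a likelihood-based mixed model fitted to all available assessments. Include arm, time as a category, and arm-by-time, with an unstructured covariance and a simpler structure named in advance in case the model does not converge. Use the same model for ObsQoR-11 at its two times.
- Report the QL-TAP and ESP-TAP contrasts at each time and averaged over times.
- State that opioid use is analysed as one 48-hour total per woman.
- State how missed assessments are handled, and that the model assumes data are missing at random.

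The cost is a paragraph of wording and a few lines of code, with no new data or visits. The downsides are small: a covariance structure must be chosen, and the missing-at-random assumption must be acknowledged in the report.
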